6.3 Study Subjects

6.3.1 Subject Disposition

Number of subjects screened, number of subjects randomized, number of subjects who took at least one dose of study medication, number of randomized subjects who complete all study visits and reasons if not will be summarized overall and by treatment group. A listing of subject disposition will be provided. Subject disposition will also be presented with a flow chart.

6.3.2 Protocol Deviations

Protocol deviations, as collected on the Protocol Deviation Form of the eCRF, will be summarized overall and by treatment group for the ITT population. A listing will also be provided.

6.3.3 Datasets Analyzed

The number of subjects in each datasets will be summarized overall and by treatment group. A listing, including reason for being excluded from a given dataset, will be provided as well.

6.3.4 Demographic and Baseline Characteristics

Demographic data and baseline characteristics such as medical history will be summarized using descriptive statistics, overall and by treatment group for the ITT population. A listing will be presented for demographic data.

6.3.5 Prior and Concomitant Medications

Prior and concomitant medications will be coded with respect to indication and generic name using the WHO Drug dictionary (version C March 2018).

Frequency of use of medications at randomization will be presented for the subjects of the ITT population by therapeutic class and preferred term, overall and for each treatment group.

A medication will be flagged as being ongoing at the time of randomization if:

- Medication start date < randomization date
AND
- Medication end date \geq randomization date OR Medication is ongoing

In case of missing or incomplete medication start / end dates, the following rules will be applied:

- If 1) the medication start date is completely missing or 2) only the year is specified and it is the same as the randomization year or 3) only the month/year are specified and they are the same as the randomization month/year, then the medication will be assumed to have started before randomization.
- If 1) the medication end date is completely missing or 2) only the year is specified and it is the same as the randomization year or 3) only the month/year are specified and they are the same

as the randomization month/year, then the medication will be assumed to have ended after randomization.

- Otherwise, partial medication start / end dates will be compared to the randomization date and the medication will be classified accordingly.

Frequency of use of prior and concomitant medications will also be presented for the subjects of the ITT population by therapeutic class and preferred term, overall and for each treatment group.

6.3.6 Treatment Compliance

An overall compliance calculation will be performed using primarily the study administration intake recorded on the Drug Accountability Form of the eCRF or on the Investigational Product Use Form of the eCRF if information regarding study medication returned/lost is missing. Compliance for the whole study is derived as follows:

| | | |
|------------------------|-----------------------|---|
| | Pill counts (%) | $\frac{[\text{sum of caplets dispensed} - \text{sum of caplets returned} - \text{sum of caplets lost}] \times 100}{[\# \text{ caplets to take per day} \times (\text{date last scheduled visit} - \text{date rando})]}$ |
| Compliance overall (%) | Days on treatment (%) | 
If # of caplets dispensed ≠ missing AND If information regarding study medication returned is missing (i.e. # of caplets returned is missing and/or # of caplets lost is missing)
 $\frac{[\text{date of last dose} - \text{date of first dose}] \times 100}{[\text{date last scheduled visit} - \text{date rando}]}$ |
| | NA | 
If # of caplets dispensed = missing OR If last scheduled visit = baseline
 |

Where

- Cohort 1 (rando number 001 à 280): Number of tablets dispensed = 147 (# caplets per day = 3)
- Cohort 2 (rando number 281 à 563): Number of tablets dispensed = 294 (# caplets per day = 6)
- Cohort 3 (rando number 564 à 997): Number of tablets dispensed = 588 (# caplets per day = 12)

Compliance will also be categorized as follow: < 80%, [80%-120%] or >120% and summarized accordingly using frequencies and percentages, by treatment arm, for the subjects of the ITT population.

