5.3 Assessment of Compliance

At each visit, all unused tablets and empty containers (bottles and kit box) should be returned by the subjects to the investigator or designee as a measure of compliance. Compliance is defined as consumption of at least 80% of the required dosage.

Accountability will be assessed by maintaining adequate IP dispensing records. The investigator is responsible for ensuring that dosing is administered in compliance with the protocol. Delegation of this task must be clearly documented and approved by the investigator.

If for any reason the IP is not administered or partially administered it should be reported in the eCRF and the reason for this must also be clearly reported in the eCRF. If this is due to occurrence of an AE the details of the event must be collected in the eCRF.

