3.2 Per-Protocol Population

The per-protocol population will include all subjects randomized, excluding subjects who were not compliant to IP and who had major protocol deviation. Subjects will be assigned to treatment groups as randomized for analysis purposes. Specific requirements are:

- Compliance of at least 80%. The compliance will be taken from the Drug Accountability Form of the eCRF.
- Absence of any major protocol deviations that could affect the primary endpoint. Those major protocol deviations are defined as:
 - “Incorrect investigational product kit administrated to subject” on Protocol Deviation Form of the eCRF

- “Subject received another investigational product” on Protocol Deviation Form of the eCRF
- Inclusion criteria “Subjects with hyperlipidemia treated with stable dose of statin for at least 6 weeks; either atorvastatin (10 mg to 20 mg daily) or equivalent dose of another statin at the time of informed consent and with LDL-C level >3.37 mmol/L (130 mg/dL) in fasting conditions at screening.” not met on Inclusion/Exclusion Criteria Form of the eCRF version previous 2.1.
- Inclusion criteria “Subjects with hyperlipidemia with LDL-C level >3.37 mmol/L (130 mg/dL) in fasting conditions at screening, treated with a stable dose of statin for at least 6 weeks or not treated with a statin at the time of informed consent.” not met on Inclusion/Exclusion Criteria Form of the eCRF version 2.1.
- Any other protocol deviations considered as major as per the sponsor.

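### A blank 'lost' field alone makes SAP 6.3.6 discard a recorded tablet return, so a subject whose returns prove under-dosing can be scored about 99% compliant by dates

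*SAP*

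**What the plan says.** Protocol 5.3 treats compliance as an amount taken, measured from the tablets brought back: "Compliance is defined as consumption of at least 80% of the required dosage". Protocol 6.2 likewise assesses it by pill count.

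SAP 6.3.6 gives the only formula for a compliance percentage. The main version subtracts returned and lost tablets from those dispensed, then divides by tablets per day times the days from randomization to the last scheduled visit. The lead sentence moves to the Investigational Product Use Form "if information regarding study medication returned/lost is missing". The table makes the trigger explicit: with the dispensed count known, the date version applies when the number "of caplets returned is missing and/or # of caplets lost is missing". The date version divides the days between first and last dose by the days from randomization to the last scheduled visit. No tablet count enters it.

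SAP 3.2 sets the per-protocol requirement: "Compliance of at least 80%. The compliance will be taken from the Drug Accountability Form of the eCRF". It does not mention the date version. SAP 6.4.4.1 repeats the primary analysis with the compliance limit lowered to 70%. Table 1.4.1 reports compliance for the ITT population in three bands: below 80%, 80% to 120%, and above 120%.

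**The concern.** The trigger treats two different gaps as one. If the return count is missing, the pill count cannot be formed and a fallback is reasonable. If only the lost count is missing, dispensed minus returned still limits how much the subject can have taken. When that limit is below the cut-off, the subject is non-compliant whatever was lost. The rule ignores this and consults dates instead.

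Dates cannot see the behaviour that returned tablets reveal. Protocol 5.1.5 and 6.2 tell subjects who miss a dose to take the next scheduled one and bring unused tablets back. Skipping doses in this way leaves the first and last dose dates unchanged, while the returns pile up.

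At stake are the accuracy of Table 1.4.1 and the meaning of the two per-protocol analyses. The 70% analysis is there to show what compliance does to the result, and a score that cannot detect skipped doses works against that aim. The protocol's definition does not repair the rule, because SAP section 1 says that the SAP prevails where the two differ.

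**Working it through.** The plan states no figure to reproduce here, so the check applies both SAP 6.3.6 formulas to the plan's own tablet counts.

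**Inputs**
- Tablets dispensed and tablets per day (SAP 6.3.6): 147 and 3 in cohort 1, 294 and 6 in cohort 2, 588 and 12 in cohort 3.
- Two kits per subject, at Week 0 and Week 6 (Protocol 5.1.1).
- Twelve weeks of treatment (Protocol 5.1.7): 12 x 7 = 84 days.

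**Are the tablet counts per kit?** 147/3 = 294/6 = 588/12 = 49 days. That covers six weeks plus the five-day visit window (42 + 5 = 47). A single kit over 84 days would cap compliance at 147/252 = 58.3%, so the counts must be per kit. Two kits give 294, 588 and 1176 tablets. The required numbers are 3 x 84 = 252, 6 x 84 = 504 and 12 x 84 = 1008.

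**Upper limit.** Compliance = (dispensed - returned - lost)/required. Since lost is at least 0, compliance is at most (dispensed - returned)/required.

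**Example, 1.5 g tier, 130 returned, 'lost' blank**
- By count: at most (294 - 130)/252 = 164/252 = 65.1%, below both 80% and 70%.
- By dates, first dose on the randomization day and last dose the day before the visit: 83/84 = 98.8%, above both.
- SAP Appendix 2 numbers randomization as day 1, so a visit on day 84 is 83 days later. The figures are then 164/249 = 65.9% and 82/83 = 98.8%, with the same classification.

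**A subject who skips half the doses throughout.** Returns are 168 of 294, 336 of 588 or 672 of 1176. The limit by count is 50.0% in every tier. The date score is 84/84 = 100% if the last dose is on the visit day. It is 82/84 = 97.6% if dosing starts one day after randomization and ends the day before the visit.

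**Returns that alone prove non-compliance over 84 days**

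| Tier | Dispensed | Proves below 80% | Proves below 70% |
|---|---|---|---|
| 1.5 g | 294 | 93 or more | 118 or more |
| 3 g | 588 | 185 or more | 236 or more |
| 6 g | 1176 | 370 or more | 471 or more |

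For instance, (294 - 93)/252 = 79.8% and (294 - 118)/252 = 69.8%.

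**What dates still catch.** A subject who stops early but attends on day 84 is found: a last dose 67 days after the first gives 67/84 = 79.8%, and 58 days gives 58/84 = 69.0%. The failure is confined to doses skipped while treatment continues.

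**The case against.** The strongest reply concerns reach.

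First, a reader might infer that known under-dosed subjects do enter the per-protocol sets. The documents do not establish that. SAP 3.2 names only the Drug Accountability Form, and nothing says that 6.3.6 overrides it. Read strictly, a date score does not satisfy 3.2, and per-protocol status with 'lost' blank is undefined. This stands. It leaves two readings, one that can admit such subjects and one that gives no answer, and both need an edit.

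Second, the annotated CRF on which the SAP rests is not among the documents. If the 'lost' field is mandatory, or zero is entered when nothing was lost, the case never arises. This also stands: the frequency is unknown. A reader might go on to put a percentage on the dilution of the per-protocol effect. That would need both the share of subjects misclassified and the effect they receive, and the documents give neither.

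Third, a reader might infer that a missing return for one kit throws away the count for the other. SAP 6.3.6 does not say whether missingness is judged per kit or on the totals, so this is only one possible reading.

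Fourth, there are other safeguards. Doses not taken must be recorded in the eCRF (Protocol 5.3). The sponsor may name further major deviations (SAP 3.2) and approves the populations before unblinding (SAP 3). These could remove such a subject, but they are discretionary and do not correct the derived value.

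**Conclusion.** The point holds as a defect in a stated rule. When 'lost' is blank and 'returned' is recorded, SAP 6.3.6 sets aside information that can settle the classification. A subject limited to 65.1% by returns can score 98.8% by dates, and a subject who takes half the doses can score between 97.6% and 100%.

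Such a subject is placed in the 80% to 120% band of Table 1.4.1. Entry to the two per-protocol sets is possible, conditional on SAP 3.2 using the 6.3.6 value.

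The conclusion assumes an 84-day interval, two full kits, accurate dispensed and returned counts, and doses skipped throughout rather than stopped early. It excludes subjects whom the SAP scores as not applicable, because the dispensed count is missing or baseline is their last scheduled visit. The effect is limited to one descriptive table and two sensitivity analyses. The primary ITT analysis does not use compliance. The number of subjects affected, and any shift in the per-protocol estimate, cannot be derived from the documents.

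**What to change.** In SAP 6.3.6, restrict the date-based version to subjects whose return count is missing. When only the lost count is missing, compute (dispensed - returned)/required and flag it as an upper limit. Never classify a subject as compliant, at 80% or at 70%, when that limit is below the cut-off. In SAP 3.2, state whether per-protocol compliance is the 6.3.6 value, including its fallback, or the Drug Accountability Form count alone.

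The cost is one line in 6.3.6, a clarification in 3.2 and a small change to the derivation program, made before the populations are approved and the data unblinded. The downside is small: subjects with unknown losses are scored at their highest possible intake, and the flag lets them be reported separately. If 'lost' is always completed, the change alters no result.

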6.4 Efficacy Analysis

Unless otherwise specified, all efficacy analyses will be conducted on the ITT population.

6.4.1 Primary Analysis

The primary endpoint is the change from Week 0 to Week 12 in direct-measured LDL-C. The changes, as well as the LDL-C values at each study visit, will be summarized with descriptive statistics.

The primary endpoint will be compared between treatment groups using a repeated measures analysis of covariance (ANCOVA) model.. More specifically, the dependent variable will be the change from Week 0 in LDL-C (change calculated as post Week 0 level – Week 0 level) the model will include treatment group, time (Week 6 and Week 12) and treatment group x time interaction as well as the covariates of Week 0 value of LDL-C and Week 0 value of LDL-C x time interaction. An unstructured covariance structure will be

used to model the within-patient errors and the Kenward-Roger approximation will be used to estimate denominator degrees of freedom. Contrasts under this model will allow for the three main comparisons: placebo vs. beta-glucan 1.5 g, placebo vs. beta-glucan 3 g and placebo vs. beta-glucan 6 g. More specifically, the following hypotheses will be tested:

$$H_0: \Delta_{W12,\text{placebo}} = \Delta_{W12,1.5g} \quad \text{vs.} \quad H_1: \Delta_{W12,\text{placebo}} \neq \Delta_{W12,1.5g}$$

$$H_0: \Delta_{W12,\text{placebo}} = \Delta_{W12,3g} \quad \text{vs.} \quad H_1: \Delta_{W12,\text{placebo}} \neq \Delta_{W12,3g}$$

$$H_0: \Delta_{W12,\text{placebo}} = \Delta_{W12,6g} \quad \text{vs.} \quad H_1: \Delta_{W12,\text{placebo}} \neq \Delta_{W12,6g}$$

where $\Delta_{W12,\text{placebo}}$, $\Delta_{W12,1.5g}$, $\Delta_{W12,3g}$ and $\Delta_{W12,6g}$ are respectively the mean change from Week 0 to Week 12 in LDL-C in the placebo, beta-glucan 1.5 g, beta-glucan 3 g and beta-glucan 6 g group.

All sets of hypotheses will be tested at the 0.0167 significance level to maintain the overall type I error to 0.05 for the primary endpoint. These tests will be considered as the primary analysis of the study.

For illustrative purposes, changes within groups will be tested at the 0.05 significance level. Estimates of the changes within groups and of the between-group differences will also be presented along with 95% confidence intervals.

The same ANCOVA model will also allow for the examination of the change from Week 0 to Week 6 in LDL-C. In other words, the hypotheses described above will also be tested at Week 6 at the 0.05 significance level for illustrative purposes.

Because the SAS procedure PROC MIXED will be used, subjects with missing data at a given study visit will not be excluded from the analysis.

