4.1 Inclusion Criteria

Subjects must meet ALL of the following inclusion criteria in order to be eligible for this study:

1. Male or female ≥ 18 years of age
2. Subjects with hyperlipidemia with LDL-C level >3.37 mmol/L (130 mg/dL) in fasting conditions at screening, treated with a stable dose of statin for at least 6 weeks or not treated with a statin at the time of informed consent.
3. Subjects willing to maintain stable standard cholesterol lowering diet (Appendix 1) and physical activity level throughout the study
4. Female of childbearing potential must have a negative urine pregnancy test at screening and randomization baseline Visit 2

Women are considered not of childbearing potential if they:

- a. Have had a hysterectomy, a bilateral oophorectomy or tubal ligation prior to Baseline Visit.
- b. Are postmenopausal defined as no menses for at least 1 year and have a serum FSH level of 40 IU/L.

Women of childbearing potential must agree to use an effective method of birth control throughout the study. Acceptable means of birth control include: implantable contraceptives, injectable contraceptives, oral contraceptives, transdermal contraceptives, intrauterine devices, male or female condoms with spermicide, abstinence, or a sterile sexual partner

5. Ability and willingness to give written informed consent and to comply with the requirements of the study

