6.2 Randomization and Treatment Procedures

Urine pregnancy test is repeated in females of childbearing potential at the randomization Visit 2.

Subjects considered by the investigator to meet all entry criteria are scheduled for randomization at Week 0 (Visit 2) where subject receives either CP105F (1.5 g, 3 g or 6 g) or matching placebo in a double-blinded fashion. Dietary counselling per Appendix 1, and IP and statin (for subjects who are taking statins) administration instructions are reviewed with the subject at each dispensing visit (Visits 2 and 3), and IP and statin (for subjects who are taking statins) compliance is assessed at subsequent visits (Visits 3 and 4):

- IP administration: 1, 2 or 4 tablets (based on the dosing arm currently recruiting) taken TID in the morning before breakfast, at mid-day before lunch and before supper time preferably at the same times every day. Subjects should be clearly instructed that if a dose is missed, the next regularly scheduled dose should be taken and unused tablets returned at the next study visit.
- Statin administration (for subjects who are taking statins): in the evening or least 2 hours after the last dose of IP.

During the 12-week treatment period, visits will take place at Weeks 6 and 12 (Visit 3 and 4 respectively, \pm 5 days), followed by a Safety Follow up (Visit 5, \pm 5 days) at Week 14.

Subjects will continue to receive dietary counselling throughout the course of the treatment period and have labs measured as outlined in Appendices 2 and 3. Subjects will be assessed for compliance to IP through pill counts (see section 5.3). At each visit, subjects will be questioned in a non-specific manner for the occurrence of Adverse Events.

Safety assessments may be done at any time during the subject's participation in the study. Follow-up phone call will be performed 2 weeks after last dose taken for capturing any AEs.

6.3 Medical History:

Medical History will consist of detailed information, with particular attention to identify factors that would exclude a patient, including: age, race, sex, current medications, drug sensitivities or any adverse reactions to medications, history of hepatic, renal, or cardiovascular disease,

smoking history, alcohol intake, drug abuse, prior hospitalizations, surgeries, interventions, and serious illnesses

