2 STUDY DESCRIPTION

2.1 Study Design

This is a Phase 2, double-blind, randomized, multicenter, 12-week comparative study of beta-glucan versus placebo, in subjects with an elevated LDL-C $>3.37\text{mmol/L}$ (130 mg/dL) treated with a stable dose of statin for at least 6 weeks or not treated with a statin.

Following signature of informed consent, approximately 264 subjects (66 subjects per beta-glucan treatment group and 22 subjects per matching placebo group) meeting all inclusion criteria and no exclusion criteria will be randomized to receive one of the three doses of beta-glucan (1.5 g, 3 g or 6 g daily) TID or a matching placebo.

The subjects will be assigned to the three different doses of beta-glucan or placebo in a tiered fashion as follows:

- The first set of 88 subjects randomized will receive either 1.5 g beta-glucan (1 tablet of 500 mg TID) or a matching placebo in a 3:1 ratio,
- The next set of 88 subjects randomized will receive either 3 g of beta-glucan (2 tablets of 500 mg TID) or a matching placebo in a 3:1 ratio,
- The last set of 88 subjects randomized will receive either 6 g of beta-glucan (4 tablets of 500 mg TID) or a matching placebo in a 3:1 ratio.

The duration of treatment is twelve weeks with beta-glucan 1.5 g, beta-glucan 3 g, beta-glucan 6 g (total daily dose) or matching placebo. Each subject is expected to participate for about 15 weeks (up to 1 week of screening, 12-weeks of treatment and follow-up call 2 weeks after last dose taken).

[figure not shown]
[figure not shown]
[figure not shown]
At baseline Visit (Week 0), the subjects should be already on a standard cholesterol lowering diet (American Heart Association Guidelines) and they should maintain it throughout the study. Subjects are encouraged to pursue a healthy lifestyle. The subjects must abstain from/minimize alcohol (EtOH) intake and keep stable any other variables that may alter serum lipid levels (e.g., strenuous exercise, weight loss programs, drugs including over the counter preparations that may alter serum lipid levels).

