6.2 Statistical Considerations

This is a randomized, parallel study with four treatment groups (placebo, beta-glucan 1.5 g, beta-glucan 3 g and beta-glucan 6 g). The statistical analysis will focus on the comparisons of the three active groups vs. placebo.

Descriptive statistics of all study variables will be presented overall and broken down by treatment group. Number of observations, mean, standard deviation, median, minimum and maximum will be presented for continuous variables. Count and proportion will be displayed for categorical variables.

Basic assumptions of the proposed analyses will be checked and data transformation or other analyses could be done if appropriate. For example, as some endpoints are likely to be skewed (ex. triglycerides, hsCRP), log-transformation might be used, in which case descriptive statistics would also include geometric means.

Laboratory parameters will be assigned to visits based on number of days from randomization and not based on scheduled visit at which the measurement was made. The time windows that will be used to assign measurements to visits are given in Appendix 2.

Values entered as less than a specified value will be considered as the specified value divided by 2 (e.g. entered value <0.2 will be analyzed as 0.1). Values entered as BLQ (Below Limit of Quantification) will be considered as the limit of quantification divided by 2. Values entered as more than a specified value will be considered as the specified value.

All statistical tests will be two-sided. Tests involving the comparisons of the active groups vs. placebo for the primary endpoint will be conducted at the 0.0167 significance level. All other tests will be considered secondary or exploratory and will be conducted at the 0.05 significance level.

No interim analysis on efficacy endpoints is planned for this study.

Statistical analyses will be done using SAS version 9.4 or higher.

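### Each dose is randomized only against its own cohort's 22 placebo subjects, yet the primary test pools placebo over three successive cohorts with no cohort or statin term and no planned report of placebo change by cohort

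*SAP*

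**What the plan says.** SAP 2.1 (and Protocol 3.1) describes tiered enrolment: "The first set of 88 subjects randomized will receive either 1.5 g beta-glucan (1 tablet of 500 mg TID) or a matching placebo", allocated 3:1; a second 88 follow for 3 g and a third 88 for 6 g. That is 66 active and 22 placebo subjects per cohort. Protocol 6.2 confirms that one dose recruits at a time, since subjects take "1, 2 or 4 tablets (based on the dosing arm currently recruiting").

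The analysis does not follow that structure. SAP 6.2 states "This is a randomized, parallel study with four treatment groups (placebo, beta-glucan 1.5 g, beta-glucan 3 g and beta-glucan 6 g"), with placebo as a single group. In SAP 6.4.1 "the model will include treatment group, time (Week 6 and Week 12) and treatment group x time interaction as well as the covariates", namely baseline LDL-C and baseline LDL-C x time. There is no cohort term and no statin term. Each dose is tested against the single placebo group at 0.0167 "to maintain the overall type I error to 0.05 for the primary endpoint".

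SAP 3.2 shows that entry criteria changed. One criterion reads "Subjects with hyperlipidemia treated with stable dose of statin for at least 6 weeks; either atorvastatin (10 mg to 20 mg daily") or an equivalent dose of another statin, recorded as "not met on Inclusion/Exclusion Criteria Form of the eCRF version previous 2.1". The current criterion (Protocol 4.1) admits subjects "treated with a stable dose of statin for at least 6 weeks or not treated with a statin at the time of informed consent". Neither document says when the change fell relative to the cohorts.

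Cohort appears in the SAP only in the compliance formula (6.3.6), by randomization-number range. Statin use appears as a subgroup factor (6.4.5). The sensitivity analyses (6.4.4) vary compliance or fit a dose curve with no covariates. No title in SAP section 7 shows placebo change by cohort.

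**The concern.** Randomization makes a dose comparable with the 22 placebo subjects of its own cohort. It does not make it comparable with the 44 enrolled alongside the other doses. Pooling is unbiased only if expected 12-week change under the same treatment, given Week 0 LDL-C, is the same in every cohort. The plan neither states nor examines this.

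If it fails, the cohort difference enters the dose-placebo contrast and can mimic or hide an effect. The documented route is statin mix. Other drift is possible but undocumented. The single central laboratory (SAP 5.6) and the stable-diet instruction (SAP 2.1) limit it, and a constant laboratory offset cancels in change from Week 0. Dose also rises in step with cohort, so the dose-response model in 6.4.4.2 is exposed to the same problem.

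**Working it through.** **Inputs from the documents.** Difference 0.30 mmol/L, SD of change 0.50, two-sided 0.0167, 60 evaluable per group, 66 randomized per group (SAP 6.1); 66:22 within cohort (SAP 2.1). About 9% loss leaves 60 active and 20 placebo evaluable per cohort.

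**Assumed inputs.** Statin shares by cohort, the difference in change between statin users and non-users, and any other drift. The documents give none of these. The calculations use Week 12 only.

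**1. The plan's own figure.** Noncentral t, 60 vs 60: power 0.803. The stated 60 per group reproduces, but only with placebo pooled.

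**2. Precision.**
- Pooled SE = 0.5 x sqrt(1/60 + 1/60) = 0.0913.
- Concurrent SE = 0.5 x sqrt(1/60 + 1/20) = 0.1291, a ratio of 1.41. Power for 0.30 is 0.455, or 0.467 with error variance pooled over all arms.
- SE of pooled minus concurrent = 0.5 x sqrt(1/20 - 1/60) = 0.0913, so its 95% CI is +/-0.179.

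**3. Bias from statin mix.** Bias for dose k = (difference in change by statin use) x (statin share in cohort k - mean share). With shares 100/50/50% the mean is 66.7%. The 1.5 g arm then has bias 0.1 x 0.333 = 0.033, or 0.2 x 0.333 = 0.067. With 100/100/50% the 6 g arm has the same size of bias.

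**4. Error rates.** Simulation of 40,000 trials with no drug effect. False benefit means a significant result favouring at least one dose.

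| Case | Any rejection | False benefit |
|---|---|---|
| No cohort difference | 4.4% | 2.2% |
| Statin difference 0.1, either set of shares | 5.3-5.5% | 2.7-2.9% |
| Statin difference 0.2, either set of shares | 8.3-8.6% | 3.7-4.8% |
| Same cases, statin in the model | 4.4-4.5% | 2.3% |

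**5. Power, true 0.30 at every dose.** When the bias opposes the effect, power in the most affected arm falls from 81% to 69% (difference 0.1) or 55% (0.2). With statin in the model it is 75-80% by arm.

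**6. Generic drift, illustration only.** Drift of 0.05 or 0.10 mmol/L per cohort gives familywise error of 7.9% or 19.5%. A one-off 0.15 shift after cohort 1 gives about 15%, with false benefit 5.6% if LDL-C then falls more and 9.5% if it falls less. With cohort in the model, error is 4.9% in all four cases.

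**7. Dose-response model.** Under the SAP's quadratic-first rule, a false linear slope appears in 5.9-6.5% (statin difference 0.1) or 9.5-11.6% (0.2) of trials, and in 4.6-4.9% with statin added. Adding cohort raises the linear SE from 0.0145 to 0.0188 (1.29 times) and the quadratic SE from 0.0081 to 0.0131 (1.62 times).

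**8. Pooled or concurrent as primary?** Mean squared error is 0.0913² + bias² for pooled and 0.1291² for concurrent. Pooled is better unless |bias| exceeds sqrt(0.1291² - 0.0913²) = 0.091. The statin cases reach 0.067.

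**The case against.** The best counter-argument is that statin mix is already addressed. The subgroup model in SAP 6.4.5 contains statin, treatment, their interaction and Week 0 LDL-C, and within a statin stratum the mix cannot bias the contrast. Since assignment within a cohort is random, the statin share in each dose column of Table 1.3.1 also estimates that cohort's share. SAP 6.2 allows other analyses if assumptions fail, and all laboratory results are listed.

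This helps a reader see a statin imbalance, but it leaves the primary contrast unadjusted. The stratum estimates are labelled illustrative, and with shares 100/50/50% there is no 1.5 g subject off statin, so that stratum has no 1.5 g contrast. The clause in 6.2 commits to nothing, and listings are not an analysis.

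The size is also open to challenge. The assumed shares are extreme: they need the criterion to change at a cohort boundary. At 80/50/50%, familywise error is about 4.8% (difference 0.1) and 5.8% (0.2); at 60/50/50% it stays below 5%. A 0.1-0.2 difference is itself unsupported, because all subjects exceed the same LDL-C threshold and statin users are on a stable dose. This stands: the harm may be small. The Week 12 simulation also simplifies the planned repeated-measures model, so its percentages indicate scale and are not exact properties of 6.4.1.

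Finally, pooling is a defensible choice. That also stands, and the fix keeps it.

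**Conclusion.** The concern holds and should be fixed. The structure is certain from the documents: successive 66:22 cohorts, one pooled placebo group, no cohort or statin term in the primary model, a widened entry criterion, and no planned output of placebo change by cohort. The claim in 6.4.1 that error is held at 0.05 is therefore conditional on an assumption the plan does not state.

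The size is uncertain. In the assumed statin cases, error ranges from near nominal to 8.6%, and power in the worst arm can fall to 55%. Milder shares do little harm. The larger drift figures illustrate sensitivity and are not a forecast; nothing in the documents shows that drift occurred.

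**What to change.** Before unblinding, amend the SAP as follows.

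1. **6.4.1, model.** Add baseline statin use (DS_STATIN, already collected) and statin x time. This removes only the statin-mix part of any cohort difference.
2. **6.4.1, assumption.** Keep the pooled contrast primary and add: *This comparison assumes that, given the model covariates, the expected 12-week change under the same treatment does not differ between cohorts.*
3. **New 6.4.4.3, supportive.** Refit the primary model with cohort and cohort x time. Report each dose against its concurrent placebo, mean placebo change by cohort, and the pooled minus concurrent difference with 95% CI. Use no heterogeneity test as a gate. Call it a transparency check: with a CI of about +/-0.18 mmol/L it cannot rule out a bias of 0.10.
4. **6.4.4.2.** Keep the planned model and the quadratic-first rule, add Week 0 LDL-C and statin use, and show a cohort-adjusted version beside it as supportive.
5. **6.1.** Note that 80% power assumes no cohort difference in change under the same treatment.

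The cost is wording and a few model runs, with no extra subjects. Cohort can be derived from the randomization-number ranges in 6.3.6. Adding statin widens the primary SEs 1.01-1.07 times at the assumed shares and hardly at all if the mix is equal. The cohort-adjusted contrasts are much less precise (intervals 1.41 times wider, about 46% power for 0.30), which is why they stay supportive.
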